#### ***Safety Cohort***

The safety cohort will encompass all eligible enrolled patients who have received at least one dose of trial treatment.

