8.1. Screening

Note that written informed consent has to be obtained from the patient prior to any trial-specific intervention including any examination done specifically for screening purposes. The participating site should keep a screening log.

8.2. *HER2* mutation testing

The presence of *HER2* mutation needs to be confirmed according to the standard assay used in the local laboratory.

Appropriate molecular tests to detect clinically relevant *HER2* mutations should include direct sequencing of exon 20 of the *HER2* gene, validated PCR-based techniques, and clinically validated next generation sequencing methods, according to the standards of each laboratory. One block of FFPE material (or alternatively, 5-10 slides) from biopsy of primary tumor or metastatic lesion for each patient with *HER2* exon 20 mutation identified in the local laboratory will be subsequently sent for confirmation to the central laboratory at Medical University of Gdansk ([name], Dept. of Biology and Genetics, Collegium Biomedicaum, Medical University of Gdansk, Poland), see ***NICHE procedures manual*** for details. This biological material will be stored at the central laboratory for potential targeted next generation sequencing that includes *HER2* and other lung cancer relevant driver mutations, such as EGFR, KRAS, ALK, ROS1, RET and BRAF. Clinical impact of other coexistent molecular alterations (if they are identified) would be analysed in exploratory analyses.

For the purpose of the patient enrolment into the trial, local testing is sufficient.

8.3. *Enrolment*

Verify eligibility, and then enrol the patient by entering the relevant information into the RDE facility ETOPdata according to the information in the ETOPdata User Manual. The date the Informed Consent was signed by the patient and the date signed by the investigator are both required to complete the eligibility checklist.

8.4. *Start of afatinib*

Afatinib treatment should start within 7 days after enrolment of the patient.

9. *Investigational product*

Afatinib is the Investigational Product (IP) used in this trial. Boehringer Ingelheim will provide the IP at no cost for the entire duration of this trial.

The ***Drug Supply Manual*** will describe detailed drug supply logistics as well as labelling, packaging, handling, drug accountability and destruction of unused drugs.

9.1. *Summary of the safety profile*

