12.5. Reporting SAEs and Adverse Events of Special Interest

Drug-induced liver injuries as defined in section 9.2 are considered to be Adverse Events of Special Interest (AESIs) and are to be reported on the SAE form, within 24 hours of awareness.

Following the subject's written consent to participate in the trial, all SAEs, whether related or not related to trial drug, must be collected, including those thought to be associated with protocol-specified procedures. All SAEs must be collected that occur within 90 days of discontinuation of dosing.

All SAEs must be collected that occur during the screening period. If applicable, SAEs must be collected that relate to any protocol-specified procedure (eg, a follow-up skin biopsy). The investigator should report any SAE that occurs after these time periods that is suspected to be related to trial drug or protocol-specified procedure.

Any SAE or AESI must be reported by submitting the completed SAE Initial Report Tab in the RDE system within 24 hours of awareness.

Submission is done via the remote data entry system, or in case of unavailability, by sending the SAE form by fax to the ETOP Safety Office:

[contact]

Once the remote data entry system is available again, the SAE Tab has to be completed by the site.

The SAE/AESI outcome must be reported within 14 days after onset by online submitting the SAE/AESI Follow-up Report Tab. In case the SAE is reported as ongoing after 14 days, the follow-up report has to be submitted again with the final outcome.

The ETOP Safety Office will forward each SAE to the trial chairs and notify principal investigators of any SAR meeting the criteria for expedited reporting (SUSAR) within the timelines specified in GCP.

The local Ethics Committee must be informed by the principal investigator about SAEs according to local regulations.

The ETOP Safety Office will inform Boehringer Ingelheim Regional Drug Safety and other appropriate persons about all SAEs and AESIs at least possibly related to trial medication (per either investigator or ETOP Safety Office review) within 24 hours of receipt.

The ETOP Safety Office will record the SAE and prepare an annual safety report (DSUR, Development Safety Update Report). Listings of SAEs will be prepared as required.

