17.3. Evaluation of primary and secondary objectives

The total trial duration will be approximately 40 months including a 6 months start-up period, 24 months accrual, 6 months follow-up after inclusion of the last patient, and 4 months for preparation of the final trial report.

The final evaluation of the trial will be performed approximately 40 months after the inclusion of the first patient.

The binomial exact one-sample test will be used for evaluation of the primary endpoint (DCR) at both the interim and final analysis (if trial continues to completion) [22-25]. The conclusion will be based on examining whether or not the observed number of patients who have achieved complete response, partial response and stable disease crosses the corresponding O'Brien-Fleming boundary. Results will be presented in terms of rates together with the corresponding exact binomial 90% confidence intervals.

The secondary endpoints of Progression free survival (PFS) and overall survival (OS) will be estimated by the Kaplan Meier method. Clinical efficacy will also be described by objective response rate (ORR).

Safety and tolerability of the afatinib treatment will be presented by tabulation of the CTCAE V4 grade. The safety cohort will encompass all patients who have received at least one dose of trial treatment.

Statistical analysis of both the primary and secondary endpoints will be described in detail in the Statistical Analysis Plan (SAP) document

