#### ***Efficacy Cohort***

The efficacy cohort will include all eligible patients enrolled in the study until trial termination.

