| Best Overall Response and Objective Response Rate (ORR) for all enrolled patients (N=13) | 9      | Efficacy cohort                             | Best Overall Response, ORR | OR : The best overall response (CR or PR) across all assessment time-points according to RECIST Criteria 1.1, during the period from enrolment to termination of trial treatment. |                         | n (%)  |                         |       |
| Progression-free Survival (PFS) for all enrolled patients (N=13)                         | 10     | Efficacy cohort                             | PFS                        | PFS : time from the date of enrolment until documented progression or death without documented progression  | -                       | KM estimates: no. of patients, n(%) of PFS events, 12-week PFS (%) (95% CI), median PFS (in weeks) | Kaplan – Meier analysis |       |
| Overall Survival (OS) for all enrolled patients (N=13)                                   | 11     | Efficacy cohort                             | OS                         | OS : time from the date of enrolment until death  | -                       | KM estimates: no. of patients, n(%) of deaths, xx-weeks OS   | Kaplan – Meier analysis |       |

| Table title  | Number | Population      | Endpoint   | Time Points or how to conglomerate  | Covariates or Subgroups                      | Summary Statistics   | Formal Analysis         | Notes |
|--|--------|-----------------|--|---|--|--|-------------------------|-------|
|  |        |                 |  | from any cause  |  | (%) (95% CI), median OS (in weeks)   |                         |       |
| Section V: Translational Results                            |        |                 |  |   |  |  |                         |       |
| Translational results of central testing                           | 12     | Efficacy cohort | All biomarkers included in the central testing (wild-type, mutation detected, type of mutation detected) | Baseline  | -  | n (%)  |                         |       |
| Section VI: Exploratory Analysis of Efficacy Endpoints      |        |                 |  |   |  |  |                         |       |

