| Primary endpoint by baseline characteristics                       | 13     | Efficacy cohort | DC at 12w achieved or not for each value of baseline characteristics                                     | 12-week assessment  | Different values of baseline characteristics | n (%)  | Fisher's exact test     |       |
| Primary endpoint by prior treatment                                | 14     | Efficacy cohort | DC at 12w achieved or not for each value of prior treatment  | 12-week assessment  | Different types of prior treatment           | n (%)  | Fisher's exact test     |       |
| Primary endpoint by translational results                          | 15     | Efficacy cohort | DC at 12w achieved or not for each value of biomarkers centrally tested                                  | 12-week assessment  | Different status of biomarkers tested        | n (%)  | Fisher's exact test     |       |
| Progression-free survival (PFS) for selected subgroups of patients | 16     | Efficacy cohort | PFS  | PFS: time from the date of enrolment until documented progression or death without documented progression | ERBB2, gender, smoking status                | KM estimates: no. of patients, n(%) of PFS events, 12-week PFS (%) (95% CI), median PFS (in weekw) | Kaplan – Meier analysis |       |
| Overall survival (OS) for selected subgroups of patients           | 17     | Efficacy cohort | OS   | OS: time from the date of enrolment until death from any cause  | ERBB2, gender, smoking status                | KM estimates: no. of patients, n(%) of deaths, xx-weeks OS (%) (95% CI), median OS (in weeks)      | Kaplan – Meier analysis |       |

| Table title   | Number | Population    | Endpoint | Time Points or how to conglomerate                                  | Covariates or Subgroups              | Summary Statistics                                  | Formal Analysis | Notes  |
|---|--------|---------------|----------|---|--------------------------------------|---|-----------------|--|
| Section VII: Safety Analysis                                       |        |               |          |   |                                      |   |                 |  |
| (Serious) Adverse event overview  | 18     | Safety cohort | AE / SAE | At the end of each treatment visit, Within 24h of occurrence of SAE | -                                    | n (%) of persons who have experienced >=1 AE or SAE | -               |  |

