| Number of patients experiencing specific number of adverse events         | 19     | Safety cohort | AE       | At the end of each treatment visit                                  | -                                    | n (%)   | -               |  |
| Number of patients experiencing specific number of serious adverse events | 20     | Safety cohort | SAE      | At the end of each treatment visit, Within 24h of occurrence of SAE | -                                    | n (%)   | -               |  |
| Maximum severity of adverse events (AE/SAE) per patient                   | 21     | Safety cohort | AE / SAE | At the end of each treatment visit, Within 24h of occurrence of SAE | -                                    | n (%)   |                 |  |
| Distribution of adverse events (AE/SAE) by Grade                          | 22     | Safety cohort | AE / SAE | At the end of each treatment visit, Within 24h of occurrence of SAE | Severity grade (NCI CTCAE version 4) | n (%)   | -               | In case of multiple reports of the same AE/SAE (grouped according to CTCAE V4) for a particular patient, the |

| Table title                          | Number | Population    | Endpoint | Time Points or how to conglomerate                                  | Covariates or Subgroups | Summary Statistics | Formal Analysis | Notes                              |
|--------------------------------------|--------|---------------|----------|---|-------------------------|--------------------|-----------------|------------------------------------|
|                                      |        |               |          |   |                         |                    |                 | event is counted once.             |
| Baseline symptoms by patient         | 23     | Safety cohort | AE       | At baseline   | -                       | -                  | -               | Patients ordered by enrolment date |
| Adverse event information by patient | 24     | Safety cohort | AE / SAE | At the end of each treatment visit, Within 24h of occurrence of SAE | -                       | -                  | -               | Patients ordered by enrolment date |
| Narratives of patients with SAE      | 25     | Safety cohort | SAE      | At the end of each treatment visit, Within 24h of occurrence of SAE | -                       | -                  | -               | Patients ordered by enrolment date |

**Table 2.** Listing of Figures

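### Does limiting the safety cohort to eligible patients in SAP 2.2 drop anyone from the safety tables?

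*SAP*

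**What the plan says.** Three places define the safety cohort.

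- SAP 2.2 (Analysis Populations): "The safety cohort will encompass all eligible enrolled patients who have received at least one dose of trial treatment".
- Protocol 17.3: "The safety cohort will encompass all patients who have received at least one dose of trial treatment".
- SAP 5 (Safety Analysis) uses the same sentence as protocol 17.3.

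SAP Table 1 assigns Tables 18 to 25 to the safety cohort by name and does not say which definition is meant. The outputs are descriptive. Table 18, for example, gives "n (%) of persons who have experienced >=1 AE or SAE", and Table 19 is titled "Number of patients experiencing specific number of adverse events".

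The efficacy cohort carries the same eligibility condition: "The efficacy cohort will include all eligible patients enrolled in the study until trial termination".

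**The concern.** A safety population normally includes everyone exposed to the drug, whether or not an entry criterion was later found to be unmet. SAP 2.2 adds a condition that the protocol does not have, and it does so in the section where a programmer would look first for a population definition. SAP 7 asks a second statistician to reproduce the analysis, so two people could build different cohorts from the same SAP and both be following its text.

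If a treated patient had been judged ineligible, section 2.2 would leave that patient's events out of Tables 18 to 25. This would sit badly with protocol 12.5, under which, once consent is given, "all SAEs, whether related or not related to trial drug, must be collected". With so few patients, losing one would be visible in the percentages.

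**Working it through.** No sample size, error rate or other stated figure is at issue. The question is whether the two definitions select different patients.

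**Inputs**

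- Enrolled at closure: 13 (SAP 1.2).
- Efficacy cohort: eligible enrolled patients (SAP 2.2).
- Size of the efficacy cohort: Table 9 in the SAP listing is assigned to this cohort and its title reads "Best Overall Response and Objective Response Rate (ORR) for all enrolled patients (N=13" (closing bracket omitted). Tables 10 and 11 carry the same label and the same cohort.
- Number treated: not stated, at most 13.

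**Step 1: the two definitions.** Under protocol 17.3 and SAP 5 the cohort is all treated patients. Under SAP 2.2 it is all patients both treated and eligible. The difference is the number treated but ineligible, which cannot exceed the number enrolled but ineligible.

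**Step 2: the count.** Enrolled minus eligible = 13 − 13 = 0. The two cohorts are therefore identical, however many of the 13 were treated.

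**Step 3: is the label consistent with the rest of the documents?**

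- SAP 3.2 promises baseline data for all enrolled patients, and Table 2 assigns that output to the efficacy cohort. The SAP again treats the two groups as one.
- Protocol 8.3 has the site check eligibility before enrolling, so a patient can be enrolled and ineligible only if a fault is found afterwards. No passage reports one.
- Central HER2 testing is the obvious route to a later finding of ineligibility. However, inclusion criterion 7.1.6 asks for a locally documented mutation, and protocol 8.2 says "For the purpose of the patient enrolment into the trial, local testing is sufficient". A discordant central result would not by itself make a patient ineligible.

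**Step 4: the size if the label were wrong.** Assume all 13 were treated and one is excluded. The denominator falls from 13 to 12.

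- The largest fall in an event percentage is for an event seen only in the excluded patient: 1/13 = 7.7% becomes 0/12 = 0%.
- The largest rise is for an event seen in everyone except the excluded patient: 12/13 = 92.3% becomes 12/12 = 100%.

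Either way the shift is 7.7 percentage points. Tables 18 to 22 list only counts and percentages, so no planned interval or test would be affected.

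**The case for a change.** The best case for an edit is that a population definition should not depend on an inference from table titles. The documents never state outright that all 13 patients were eligible, or that all were treated. Nothing in the SAP says that section 5 overrides section 2.2. The SAP exists for the final analysis, which is where the cohort is used, and deleting one word would cost almost nothing.

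Much of this stands. The inconsistency is real, the sentence in 2.2 is the outlier, and dropping the word would be the right way to align it. The independent reproduction in SAP 7 would expose a difference between two programmers but would not settle which definition applies.

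What does not stand is that the edit would alter anything. This is not a forward-looking rule that may meet an ineligible patient later: SAP 1.2 and 1.3 show it was written after closure, for patients already enrolled. Reaching a wrong table would take an ineligible treated patient whom no passage reports. It would also take an analyst who follows section 2.2 against both the SAP's own safety section and the protocol.

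**Conclusion.** The wording differs, but no change to the plan is called for because there is no gain. On the documents' own figures the extra condition removes 0 of 13 patients, so every safety count and percentage is the same under either definition. Serious adverse event collection does not depend on the cohort definition, and neither the stage 1 decision nor the disease control rate uses the safety cohort.

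This rests on one assumption: that the N=13 labels on Tables 9 to 11 correctly describe the efficacy cohort, so that every enrolled patient was eligible. If that failed for one treated patient, SAP 5 and protocol 17.3 already give the analyst the rule to follow. Even if section 2.2 were followed instead, the effect on any descriptive percentage would be at most 7.7 points, assuming all 13 were treated. The point is an editorial slip, not a choice of analysis.

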## 2.3 Statistical Considerations

Primary endpoint is disease control (DC), defined as complete (CR) or partial response (PR), or disease stabilisation (SD) lasting at least 12 weeks.

Simon's two stage phase II design has been adopted. A Disease Control Rate (DCR) of 50% was considered as unacceptable, targeting a DCR of 75%. Hence the null hypothesis under consideration was that the  $DCR \leq 50\%$  versus the alternative that  $DCR \geq 75\%$ . For a one-sided type I error of 10% and power of 80%, a total of 22 patients were needed, with 9 patients in the first stage. If in the first stage, 6 out of the 9 patients achieved Disease Control, then the trial would proceed to the second stage and recruit an additional 13 patients for a total of 22 patients. If at least 14 out of the 22 patients achieved Disease Control, then this finding would indicate that it would be reasonable to proceed to a Phase III trial.

Secondary endpoints include objective response (OR), defined as best overall response (CR or PR, using RECIST 1.1 criteria) across all assessment time-points during the period from enrolment to termination of trial treatment, progression-free survival (PFS), defined as the time from the date of enrolment until documented progression or death, overall survival (OS), defined as time from the date of enrolment until death from any cause (censoring occurring at the last follow-up date), and toxicity as specified by the adverse events classified according to NCI CTCAE version 4.

## 2.4 Missing Data

Missing values will not be replaced by any statistics calculated over non-missing data.

# 3. SUMMARY OF STUDY DATA

## 3.1 MAIN OUTCOME

The primary endpoint according to study's protocol, is the **DCR**.

DCR will be calculated along with 90% exact binomial confidence interval (CI) for the efficacy cohort.

PFS and OS (medians and rates) will be estimated based on the product-limit Kaplan-Meier method, while the corresponding 95% CIs for the median values will be based on the complementary log-log transformation.

### **3.2 Baseline characteristics**

Baseline characteristics will be summarized and presented overall **for all enrolled patients.**

All continuous variables will be summarised using the following descriptive statistics: n (non-missing sample size), mean, 95% CI for the mean, median, maximum and minimum. The frequency and percentages (based on the non-missing sample size) of observed levels will be reported for all categorical measures.

### **3.3 Follow-up and treatment administration**

Follow-up time will be defined as time between the minimum of enrolment and start treatment date and last contact date. The median follow-up will be estimated based on reverse censoring of overall survival.

Time-to-Treatment Failure (TTF) will also be calculated based on the Kaplan-Meier method, and the specific reasons of treatment failures will be provided.

### **3.4 Translational results**

The results of all translational analyses (of the tests performed centrally) in the frame of the study will be analytically presented in tabular format.

## **4. EFFICACY ANALYSIS**

The primary efficacy analysis will include all eligible enrolled patients.

The primary endpoint is disease control, defined as complete or partial response or disease stabilisation lasting at least 12 weeks.

Results on the primary endpoint will be presented for the whole efficacy cohort as well as for the 'interim analysis' cohort.

Objective response, progression-free survival and overall survival, the secondary efficacy endpoints of the NICHE trial, will also be evaluated for the whole efficacy cohort.

Best overall response, defined as best response across all assessment time-points, during the period from enrolment to termination of trial treatment, and objective response rate, defined as the best overall response (complete or partial response) will be summarized in table format.

PFS (defined as the time between the minimum of enrolment and start treatment date until documented progression or death) and OS (defined as the time between the minimum of enrolment and start treatment date until death or last contact date for censored patients) will be summarized through tables as well as graphically depicted via Kaplan-Meier curves and alternative graphical illustrations if possible (spider plot, swimmer plot).

As an exploratory analysis, the association of the primary endpoint (Disease control at 12 weeks) with patients' baseline characteristics, prior treatments received as well as with translational results will be also investigated.

More particularly, the distribution of patients' baseline characteristics and prior treatments will be presented separately for the group of patients that achieved disease control at 12th week versus the group of patients that did not achieve disease control and corresponding Fisher's exact tests will be provided.

In a similar manner, all translational results will be presented separately for the groups of patients that achieved or not disease control. Also, PFS and OS results will be provided for selected subgroups of patients with particular interest (type of ERBB2 mutation, Gender and Smoking status). Log-rank test comparing the survival curves between subgroups will be also presented.

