Clinically relevant *HER2* mutations are clustered in exon 20 of the *HER2* gene and commonly include small exon 20 insertions (majority of patients), clustered or single amino acid substitutions all nested in the most proximal region of the exon, between codons 775 and 881. In the study of Arcila *et al*, the frequency of *HER2* mutations among lung adenocarcinoma patients was 26/1478 (approx. 2%). *HER2* insertions identified in this study included A775_G776insYVMA (80% of tumours), G776>VC, V777_G778insCG and P780_Y781insGSP and point mutations included L755S and G776C [9].

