4.5. Rationale for trial design

HER2 mutations are identified in about 2% of non-small-cell lung cancers (NSCLC) and appear to be critical for lung carcinogenesis. There are very few data available that describe the clinical course of *HER2* mutated NSCLC patients. Mazieres and colleagues recently retrospectively identified 65 NSCLC patients diagnosed with a *HER2* in-frame insertion in exon 20 [6]. The *HER2* mutation was almost an exclusive driver, except one single case with a concomitant *KRAS* mutation. The trial population presented with a median age of 60 years (range 31-86), a high proportion of women (45 vs. 20 men, 69%), and of never smokers (34, 52.3%). All tumours were adenocarcinomas and 50% were stage IV at diagnosis. For these latter cases, 22 anti-*HER2* treatments were administered after conventional chemotherapy in 16 patients. Subsequently, four progressive disease, seven disease stabilizations and eleven partial responses (overall response rate ORR 50%; disease control rate DCR 82%) were observed. Specifically, they observed a DCR of 93% for trastuzumab-based therapies (n = 15), 100 % DCR for afatinib (n = 3), but no response to other *HER2*-targeted drugs (n = 3). Progression free survival for patients with *HER2*-therapies was 5.1 months. Median survival was of 89.6 and 22.9 months for early stage and stage IV patients, respectively. This study, the largest to date dedicated to *HER2*-mutated NSCLC, reinforced the importance of screening for *HER2*-mutations in lung adenocarcinomas, and suggested the potential efficacy of *HER2*-targeted drugs in this population. Additionally, single case reports suggest that *HER2* mutations may be predictive for *HER2* targeting therapies in lung cancer [17-19]. Some ongoing clinical trials are enrolling patients with *HER2* mutated NSCLC, mixed together with *HER2* amplified or *EGFR* mutated NSCLC cases. Large biomarker screening programs such as the French National Program or the US Lung Cancer Mutation Consortium (LCMC) thus propose testing for *HER2* mutations.

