### 1.2 History of the Study

ETOP/7-14 NICHE trial was activated in December 2014 and the first patient was enrolled on September 2015.

The ETOP IDMC reviewed the trial safety data during its scheduled bi-annually meetings, in April 2016 (n=5 patients enrolled; no safety issues identified) and October 2016 (n=13) when the interim analysis was presented. Follow-up was suspended based on the interim analysis and an unscheduled follow-up IDMC meeting in November 2016 on the 13 enrolled patients enrolled).

At the IDMC meeting of October 2016, the interim analysis (1st stage of Simon's two-stage design) was presented. Among the first 9 patients, 5 patients (55.6%) had not reached week 12 free of progression. Thus, the stopping threshold of the 1st stage of Simon's two-stage design was reached, since more than the maximum allowed of 3 patients had a progression by 12 weeks. Based on these results, the IDMC recommended suspending further recruitment into the trial while continuing the treatment and close follow-up for the enrolled patients.

A follow-up analysis, once all enrolled patients reached the 12-week assessment, was performed in November 2016. Among all 13 enrolled patients, 6 patients (46.2%) had not reached week-12 free of progression.

Based on the data and results of the interim analysis and considering the protocol specified early stopping rule, the IDMC recommended that:

- The ETOP 7-14 NICHE trial should be permanently closed to accrual.
- Treatment and follow-up of enrolled patients may continue based on the judgement of the treating physician.
- Patients should be informed.

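### The planned log-rank tests of PFS and OS by ERBB2 mutation type use a chi-square approximation that rejects too often if, among at most 13 patients, some types hold a single patient

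*SAP*

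**What the plan says.** SAP section 4 states that "PFS and OS results will be provided for selected subgroups of patients with particular interest (type of ERBB2 mutation, Gender and Smoking status", and adds: "Log-rank test comparing the survival curves between subgroups will be also presented". In the table listing of SAP section 8, Tables 16 and 17 carry the subgroups "ERBB2, gender, smoking status" under the exploratory block. They give Kaplan-Meier as the formal analysis and do not mention the log-rank test.

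The analysis set is small and was known to be small when the SAP was written. SAP 2.2 defines it: "The efficacy cohort will include all eligible patients enrolled in the study until trial termination". SAP 1.2 reports: "Among all 13 enrolled patients, 6 patients (46.2%) had not reached week-12 free of progression". Accrual had then been closed.

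For disease control against baseline factors, prior treatment and central test results, SAP section 4 specifies Fisher's exact test. For the time-to-event comparisons it specifies no exact or permutation version, no significance level, no minimum group size and no grouping of mutation types. SAP section 7 names SAS 9.4 for the analysis.

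On the mutation types to expect, protocol 4.3 cites a series with "A775_G776insYVMA (80% of tumours), G776>VC, V777_G778insCG and P780_Y781insGSP and point mutations included L755S and G776C", that is, one dominant insertion and five other types.

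**The concern.** An unqualified log-rank test is normally read as the standard one, referred to a chi-square distribution. That reference is a large-sample approximation, and it is poor when a group contains one or two patients. The SAP protects the binary comparisons in these patients with an exact test but leaves the survival comparisons without one.

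Mutation type is the subgroup most exposed, because most patients are expected to share one insertion and the rest may be scattered. A lone patient with a rare mutation who progresses first could produce a very small p-value that the data cannot support. After early closure, such exploratory signals may be carried into later hypotheses.

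**Working it through.** **Plan's own figure.** The documents give no operating characteristic for these log-rank tests. Their only design figure, 22 patients for disease control, reproduces (type I error 0.097, power 0.807) but has no bearing here.

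**Inputs.**
- At most 13 patients (SAP 1.2, 2.2).
- 80% with the common insertion and five other types (protocol 4.3). Equal shares of 4% for the five are an assumption.
- 69% women and 52.3% never smokers in the background series (protocol 4.5), so about 9:4 and 7:6 of 13.
- Median PFS 5.1 months (about 22 weeks) and median OS 22.9 months (about 99.6 weeks) from the same series, taken as exponential.
- Scans at weeks 6, 12, 20, 28 and so on (protocol 15.5).
- Nominal 5%: a convention, since the SAP sets no level.

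**Likely layout.** 0.80 × 13 = 10.4 patients with the common insertion and 2.6 with others. The chance of at least two types is 1 − 0.8^13 = 0.945. Given that, about 91% of simulated samples contain a single-patient type, so overall 0.945 × 0.91 ≈ 0.86.

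**One patient against 12, no ties, no censoring.** If the single patient has the r-th event, E is the sum of 1/n and V the sum of (n−1)/n² over the risk sets n = 13, 12, … up to that event. The statistic is (1−E)²/V.
- First event: E = 1/13, V = 12/169, statistic = (12/13)²/(12/169) = 12.0, p = 0.0005. The exact permutation p is 1/13 = 0.077.
- Second event: E = 1/13 + 1/12 = 0.160, V = 12/169 + 11/144 = 0.147, statistic = 4.78, p = 0.029.
- All other ranks: p > 0.08.

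The true size at nominal 5% is therefore 2/13 = 15.4%. The same enumeration gives 30/156 = 19.2% for 11:1:1 and 486/1716 = 28.3% for 10:1:1:1.

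**Rejection rate under no difference, nominal 5%.** Scan-tied PFS and OS are simulated with 6,000 trials per layout and assumed uniform censoring over weeks 26-76. Untied PFS is uncensored.

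| Groups | PFS tied at scans | PFS untied | OS |
|---|---|---|---|
| 12:1 | 7.4% | 15.4% (exact) | 13.4% |
| 10:2:1 | 9.8% | 16.2% | 12.1% |
| 11:1:1 | 11.0% | 19.2% (exact) | 16.0% |
| 10:1:1:1 | 11.6% | 28.3% (exact) | 23.1% |
| 11:2 (pooled)* | 8.4% | 10.3% | 7.0% |
| 10:3 (pooled) | 6.2% | 8.8% | 4.9% |
| 9:4 (sex) | 5.5% | 7.6% | 4.6% |
| 7:6 (smoking) | 5.7% | 7.5% | 4.3% |

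*Separate run: 3,000 trials, OS censoring at weeks 26-86.

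Other runs with slightly different censoring put 10:1:1:1 at 12-13% tied, up to about 29% untied, and 23-24% for OS. Averaged over the assumed 80% mix, the rates are about 11% tied, 19% untied and 17-18% for OS. Four or five single-patient types would go higher (35% and 42% untied).

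**How tied is PFS?** Scans are counted from first dose, PFS from enrolment (or the earlier of the two dates), and treatment may start up to 7 days after enrolment. With scan dates varied by up to a week either way and 20% of events taken as deaths on their own date (both assumptions), the rates were 15.2% (12:1), 15.1% (10:2:1), 19.1% (11:1:1) and 26.8% (10:1:1:1), close to the untied column.

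**After the change.** The permutation log-rank, untied and uncensored, has size 0% for 12:1, 6/156 = 3.8% for 11:1:1 and 84/1716 = 4.9% for 10:1:1:1.

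**The case against.** The strongest reply is that the layout is assumed. The SAP speaks of "selected subgroups of patients with particular interest (type of ERBB2 mutation, Gender and Smoking status" and Tables 16-17 say only ERBB2. Nothing states that each rare variant becomes its own log-rank group, and a median and 12-week PFS with an interval per subgroup suit groups of several patients. The 80% share comes from a cited background series. This stands: the inflation is conditional on separate testing. But the SAP has no pooling rule either, so the condition is open.

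Second, the lone-first-progressor example is a corner case. If that patient ties with two others at the first scan, E = 3/13, V = 3 × (12/169) × (10/12) = 0.1775, and the statistic is (10/13)²/0.1775 = 3.33, p = 0.068. This stands for fully tied PFS. It does not help OS, which is not tied to scans, and small differences in dates undo much of it for PFS.

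Third, no decision hangs on these tests, and readers have some protection: Tables 16-17 show patients and events per subgroup, and Figure 6 shows PFS patient by patient. This limits the importance, but a p-value that is too small remains wrong in an exploratory table.

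A reader might infer that all the subgroup log-rank tests are badly inflated, or that this trial will certainly have single-patient types. The documents support neither: sex and smoking stay near nominal, and the trial's own mutation types are not given.

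**Conclusion.** The point holds in a limited form. If ERBB2 types are compared as separate groups and some contain one patient, the chi-square log-rank test at nominal 5% rejects under no difference about 7-13% of the time for fully scan-tied PFS, about 15-29% for untied times and about 12-24% for OS, for layouts with one to three single-patient types. Pooled as common insertion against other, it is about 5-10%; for sex and smoking, about 4-8%.

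These figures assume the standard chi-square version of the test, a 5% level that the SAP does not set, exponential times with the cited background medians, and assumed censoring. That single-patient types are likely rests on the background mix with equal shares for the rarer types.

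The analysis is exploratory and cannot change the primary disease-control conclusion. This is a cheap improvement of minor severity.

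**What to change.** In SAP section 4, replace the unqualified log-rank test by an exact or Monte Carlo permutation log-rank p-value, and enter it as the formal analysis in Tables 16 and 17. For ERBB2, compare the common insertion with all other exon 20 mutations as two groups, and describe single-patient types without a p-value. The pooling rule does most of the work. Applying the permutation version to sex and smoking as well gains little there but uses the same code.

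The cost is one or two SAP sentences and a few lines of SAS or R; if R is used, SAP section 7, which foresees it only for plots, needs a word added. No new data are needed. The downside is that some exploratory p-values become larger, and with a 12:1 split the exact test cannot reach 5% at all (smallest p = 0.077). That is a fair statement of what one patient can show.
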